1. For each experimental SSI, researchers hypothesize that participants assigned to the SSI will report a different extent of change in depressive symptoms from baseline to four-week follow-up than participants in the active comparison condition.
2. For each SSI, researchers hypothesize that participants assigned to the SSI will report a different extent of change in each secondary well-being outcome (agency, hopelessness, depression change expectancies, readiness for change, frequency of positive actions and thoughts) compared to participants in the passive control. researchers will compare change in all outcomes from baseline to four-week follow-up, as well as from baseline to immediate post-intervention for outcomes collected at all three timepoints.
3. For each experimental SSI, researchers hypothesize that participants assigned to the SSI will report a different extent of change in each secondary well-being outcome (from baseline to week four or baseline to post-intervention) than those assigned to the active comparison condition.
4. For each experimental SSI, researchers hypothesize that participants will rate the SSI as differently acceptable than the active comparison SSI according to CEQ scores, star ratings, and rate of Aha! Moments.
5. We hypothesize that participants who expect they can improve their depression more at baseline will show a different change in depressive symptoms from baseline to week four.
6. We hypothesize that, on average, the SSIs will be more effective at improving all well-being outcomes (from baseline to week four or baseline to post-intervention) than the passive control.

We do not make any specific hypotheses about which SSIs will be more effective or acceptable than others.

Statistical Analysis Plan

Inclusion criteria

Participants will need to be at least 18 years old, be able to read and write fluently in English, and have enough access to the internet to complete two sessions over four weeks. They must also score at least 10 on the PHQ-9 screen (suggesting moderate depression) and pass the bot check (<https://osf.io/kba7v>) during the screen (Kroenke et al., 2001).

All participants who are randomized to an experimental condition (and therefore completed all baseline measures) will be included in analyses. If a participant begins a survey multiple times, researchers will only keep data from the first time.

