Please see the measures document (<https://osf.io/76cfy>) and the data cleaning script (<https://osf.io/jpk38>) for details on measures and recoding. Before sharing the study data, researchers will remove any potentially identifiable information, included in written response items. Deviations from this pre-registration will be documented.

References:

Primary analysis

Researchers will use a mixed-effects linear regression model to test if depressive symptoms decrease more from baseline to four-week follow-up in each of the 12 active conditions compared to the passive control condition. Timepoint is a three-level factor (i.e., baseline, post-test, and week 4 follow up). The model will include a participant identifier as a random intercept.

Using the “lme4” and “lmerTest” packages in R, this analysis will take this form:

```
lmer(depressive_symptoms ~ timepoint * condition + (1|participant_id))
```

Using lmerTest’s default, p-values will be calculated using Satterthwaite’s method for denominator degrees of freedom.

Secondary analyses (matching the hypotheses above):

1. To test if each experimental SSI changes PHQ-9 scores differently from the active comparison SSI, researchers will redo the main analysis, except using the active comparison condition as the comparator.

2. To test if each SSI changes secondary well-being outcomes to a different extent than the passive control, researchers will replicate the primary analysis for each secondary outcome. For outcomes measured at three timepoints, researchers will compare baseline to each timepoint.
3. To test if each experimental SSI changes secondary well-being outcomes to a different extent than the active comparison SSI, researchers will redo analysis #2, but instead use the active comparison SSI as the comparison condition.
4. To test if each experimental SSI differs in acceptability from the active comparison SSI, researchers will conduct a linear regression model testing between-group differences in intervention acceptability for each acceptability outcome at each timepoint the outcome was collected. For these analyses, researchers will drop data from the passive control because it does not make sense to compare satisfaction with a mental health intervention to satisfaction with an educational program about trout.

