5. To test if participants who expect that they can change their depression more at baseline will show a different reduction in depressive symptoms from baseline to week four, researchers will run a linear mixed-effects regression model with depressive symptoms as the DV, timepoint, baseline depression expectancies, and the interaction between the two as predictors, and a participant identifier nested in experimental condition as a random intercept.
6. To test if, on average, the SSIs will change each outcome differently than the passive control, researchers will re-run the main analysis with *experimental condition* re-coded into a two-level factor in which any of the 12 active SSIs will be coded as “active.” The random intercept, participant ID will be nested within experimental condition. For outcomes measured at three timepoints, researchers will compare the baseline to each timepoint

Sensitivity analyses:

1. Researchers will re-run the primary analysis with demographic covariates: age, gender, disability, race, education, relationship status, political party, employment status, household income, and perceived socioeconomic standing (Social Ladder).
2. Researchers will re-run the primary analysis with demographic and baseline mental health covariates: age, gender, disability, race, education, relationship status, political party, employment status, household income, perceived socioeconomic standing (Social Ladder), baseline depression change expectancies, baseline

positive actions and thoughts, baseline readiness for change, baseline agency, and baseline hopelessness.

3. Researchers will test for differential attrition across conditions and by the interaction of condition and each covariate. If researchers find evidence for differential attrition, researchers will conduct a sensitivity analysis re-running primary and secondary analyses accounting for differential attrition using inverse probability weighting. See the analysis script (<https://osf.io/5eya3>) for details.

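### Sensitivity analyses 1 and 2 name no timepoint-by-covariate term; entered as main effects, their covariates cancel from the tested contrast, so agreement with the primary result is largely built in

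*Combined protocol and SAP*

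**What the plan says.** The primary model (Statistical Analysis Plan, Primary analysis) is "lmer(depressive_symptoms ~ timepoint * condition + (1|participant_id", closed by the final brackets. Its purpose is to "test if depressive symptoms decrease more from baseline to four-week follow-up in each of the 12 active conditions compared to the passive control condition". The only random effect is the participant intercept: "The model will include a participant identifier as a random intercept".

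Under Sensitivity analyses, item 1 reads "Researchers will re-run the primary analysis with demographic covariates" and lists ten variables. Item 2 reads "Researchers will re-run the primary analysis with demographic and baseline mental health covariates" and lists the same ten plus five baseline scores: change expectancies, positive actions and thoughts, readiness, agency and hopelessness. Neither item gives a formula or mentions an interaction.

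Secondary analysis 5 does name one. Its model has "timepoint, baseline depression expectancies, and the interaction between the two as predictors". It serves secondary hypothesis 5, that "participants who expect they can improve their depression more at baseline will show a different change in depressive symptoms".

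Item 3 of the sensitivity analyses covers dropout: "Researchers will test for differential attrition across conditions and by the interaction of condition and each covariate". If such attrition is found, inverse probability weighting follows. An analysis script is linked there, but its content is not part of the document.

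**The concern.** The tested quantity is a difference between arms in change over time. A covariate that is constant within a participant can adjust that quantity only if its effect is allowed to differ by timepoint. The plan spells out such a term in secondary analysis 5 and not in sensitivity analyses 1 and 2, so main effects is the natural reading of those two items.

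On that reading, a report that the 12 comparisons were unchanged after adjustment for 15 covariates would mostly describe the algebra. Readers would take it as evidence that chance imbalance in predictors of change did not matter, which the analysis cannot show. There is also an internal tension. Hypothesis 5 links baseline change expectancies to change in depressive symptoms, yet sensitivity analysis 2 adds that variable without naming the term needed to adjust change for it.

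**Working it through.** **Inputs from the plan.** 500 participants per SSI arm and 1,500 in the passive control (Sample Size). Random-intercept model with timepoint * condition (Primary analysis). Missing outcome scales are not imputed and missing covariates are (Missing data handling), so adjustment does not change the analysed sample. The plan gives no dropout rate, baseline-to-week-4 correlation or covariate strength; those are assumed below.

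**1. The plan's own figure.** For 500 vs 1,500, SD 1, two-sided alpha 0.05 and 90% power, the detectable d is (1.960 + 1.282) × √(1/500 + 1/1500) = 3.242 × 0.0516 = 0.167. This agrees with the stated 0.17 (power at 0.17 is 0.909). The factor 0.052 is also the chance SD of a standardised covariate difference between an SSI arm and control.

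**2. Algebra with main effects.** Write participant i's score at time t as y_it = μ_t + α_t·c_i + w_i′γ + b_i + e_it, with arm indicator c_i, covariates w_i and random intercept b_i. The change from baseline to week 4 is

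y_i,wk4 − y_i,base = (μ_wk4 − μ_base) + (α_wk4 − α_base)·c_i + (e_i,wk4 − e_i,base).

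Both w_i′γ and b_i cancel. With baseline and week 4 observed for everyone, the estimate is the difference in mean change whatever covariates are added. With complete data the SE is also unchanged, as long as the between-person variance estimate is above zero. A third timepoint does not alter this: the contrast weights (−1, 0, 1) still sum to zero within each participant.

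**3. Algebra with timepoint-by-covariate terms.** Change now contains w_i′η, and the adjusted estimate is the unadjusted one minus η′(w̄_arm − w̄_control). If the covariates explain a share R² of change variance, that correction has SD of about √R² in SE units and mean absolute size of about √(2/π) × √R² = 0.798 × √R².
- R² = 5%: 0.798 × 0.224 = 0.18 SE; SE ratio √0.95 = 0.975.
- R² = 10%: 0.798 × 0.316 = 0.25 SE; SE ratio √0.90 = 0.949.

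**4. Simulated full design.** 12 × 500 + 1,500 participants, 15 covariates, no true effect, REML fits, versions with two and with three timepoints. There were 80 datasets per scenario (60 for the strong case). Assumed: covariates explain 20% of baseline variance and 5% or 10% of change variance; correlation 0.5. Entries are average absolute shifts from the primary estimate, in SE units.

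| Week-4 data | Main effects | Timepoint * covariate |
|---|---|---|
| Complete | below 1e-13; SE ratio 1.0000; 0 of 12 verdicts change | 0.19–0.31; 0.3–0.6 of 12 verdicts change |
| 20–35% dropout depending on covariates | 0.05–0.13 | 0.21–0.33 |
| 20–35% dropout, moderate condition-by-covariate dependence | 0.29–0.40 | – |
| 20–30% dropout, strong condition-by-covariate dependence | 0.72–0.98 | – |

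Across the first two rows, main effects removed −5% to +1% of the chance imbalance in predictors of change, and interactions removed 90% to 101%. The SE ratio with interactions was 0.946–0.976, matching step 3. At change R² 10%, two timepoints and 35% covariate-dependent dropout, the main-effect shift had mean 0.13, 95th percentile 0.33 and maximum 0.67 SE.

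**5. A second simulation under different assumptions.** One SSI arm of 500 vs 1,500, 15 covariates, 300 trials per scenario, outcome SD 5, intraclass correlation 0.55, true effect −0.85 points. Covariates explain 30% of between-person variance. A covariate-related slope adds variance equal to 15% of the residual change variance.
- Complete data: main effects changed nothing, with no disagreement on significance. Interactions moved the estimate by 0.31 SE on average (maximum 1.07), cut the SE from 0.262 to 0.246 and changed significance in 6% of trials.
- Random dropout of 10/20/30%: main effects moved it by 0.06/0.08/0.11 SE, interactions by 0.30/0.32/0.34 SE.
- Dropout depending on condition by covariate, 20%: primary −1.081, main effects −1.008, interactions −0.839. Share of bias removed by main effects: (1.081 − 1.008)/(1.081 − 0.85) = 0.073/0.231 = 32%.
- The same at 30%: −1.179, −1.095 and −0.838. Share removed by main effects: 0.084/0.329 = 26%. Interactions removed essentially all of the bias in both cases.

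**The case against.** The formula is unstated, not wrong. The linked analysis script, which is not in the document, may already contain the interactions. The plan also never says what sensitivity analyses 1 and 2 are for, so testing chance imbalance in predictors of change is an aim supplied by the reader. Main-effect covariates have another legitimate use: with outcomes left unimputed, they let the missing-at-random assumption condition on more variables. An online study with a four-week follow-up will have dropout, and when dropout depends on condition by covariate the main-effects re-run does move, by 0.29 to 0.98 SE on average in step 4. Finally, no decision in the plan rests on these two analyses, and hypothesis 5 concerns only one of the 15 covariates.

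Much of this is fair and limits the scope. The script could settle the matter, which is why the conclusion is conditional. The response to condition-by-covariate dropout is real, but main effects removed only a quarter to a third of that bias in step 5, and item 3 already addresses such attrition by weighting. What remains is that the text, followed as written, gives two adjusted analyses that barely adjust the quantity being tested. Without a stated aim or formula, a reader will take agreement as robustness.

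**Conclusion.** The concern holds, on the condition that covariates enter as main effects. Exact agreement with the primary under complete data is algebraic and needs no assumption about SDs, correlations or covariate strength beyond a positive between-person variance estimate. With random or covariate-dependent dropout of 10–35%, agreement is close: average shifts of 0.05–0.13 SE, against 0.21–0.34 SE with timepoint-by-covariate terms. Those sizes rest on the assumed covariate strength, correlation and dropout. Agreement is not guaranteed when dropout depends on condition by covariate.

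The reach is limited. The primary estimate and its SE remain valid and already allow for chance imbalance. Only the interpretation of two planned robustness checks is affected.

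**What to change.** Write out the formulas for sensitivity analyses 1 and 2 and include timepoint * covariate for every covariate, keeping the random intercept and all available rows. If the linked analysis script already does this, say so in the plan text.

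If main effects are intended, add one sentence stating that these analyses can differ from the primary only through missing outcome data, chiefly at week 4, and do not report agreement as robustness to covariate imbalance.

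An ANCOVA of the week-4 score is an alternative. It drops participants without that score, so it changes the missing-data handling as well as the adjustment.

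The cost is a formula or a sentence, with no new data and no change to the primary analysis. With three timepoints, 15 single-column covariates add 15 × 2 = 30 interaction terms. Dummy coding of categorical variables adds more, still few against 7,500 participants.

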Robustness Check: Researchers will not correct for multiple hypotheses in primary and secondary analyses because each test of an intervention's effect is viewed as a separate hypothesis. However, it might be that some statistically significant results detected are false positives that occur due to testing so many hypotheses at once. To examine this possibility, researchers will conduct a robustness check that replicates all analyses that compare an outcome across many conditions correcting for multiple hypotheses using the Benjamini-Hochberg procedure (Benjamini & Hochberg, 1995).

Inference Criteria: P-values will be used as the criterion for statistical significance. Two-sided tests will be used for all analyses. Effects of $p \leq .05$ will be reported as significant, $.05 < p \leq .1$ as marginally significant, and $p > .1$ as nonsignificant.

Missing data handling: Because participants can choose to skip items, there may be some missing data within outcome measures. If one's response to a scale is missing 33% of its items or fewer, researchers will impute a value for each missing item using the mean of the other items of the scale that the participant answered.

If an outcome scale is missing more than 33% of its items, researchers will consider the entire scale to be missing. In these cases, researchers will not impute missing outcome data because linear mixed models' estimates for longitudinal clinical trial data are not improved by outcome data imputation (Chakraborty & Gu, 2009). Researchers will impute missing covariate data as described in the cleaning script (<https://osf.io/jpk38>).

Sample Size: Researchers will aim to recruit 500 participants per intervention condition, except that the passive control condition will have 3X as many participants as the other conditions because it will improve the statistical power of analyses comparing conditions to the passive control. Thus, researchers aim for a total baseline sample size of $n = 7,500$. This sample size will enable us to detect change in depressive symptoms from baseline to follow-up between each intervention condition and the passive condition with an effect size smaller than Cohen's $d = 0.17$, with 90% power and alpha = 0.05. This sample size will also allow us to detect differences in change in depressive symptoms from baseline to follow-up between each intervention condition smaller than $d = 0.19$.

References:

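### The weighted re-analysis for dropout is run only if attrition tests show evidence of a difference, so for small to moderate excess loss in one arm its appearance depends largely on chance

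*Combined protocol and SAP*

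**What the plan says.** The Sensitivity analyses section, item 3, sets out two steps. The first is unconditional: "Researchers will test for differential attrition across conditions and by the interaction of condition and each covariate". The second depends on the first: "If researchers find evidence for differential attrition, researchers will conduct a sensitivity analysis", which consists of "re-running primary and secondary analyses accounting for differential attrition using inverse probability weighting". Details are left to a linked analysis script.

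The text does not say what counts as evidence. It gives no p-value cut-off for these tests, no rule for combining them, no multiplicity rule and no size of difference. The Inference Criteria paragraph supplies a general standard, "P-values will be used as the criterion for statistical significance", with p ≤ .05 called significant and a further band up to .1 called marginally significant.

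Item 3 does not list its covariates. Items 1 and 2 of the same section name ten demographic variables ("age, gender, disability, race, education, relationship status, political party, employment status, household income, and perceived socioeconomic standing (Social Ladder") and five baseline mental health measures: depression change expectancies and "positive actions and thoughts, baseline readiness for change, baseline agency, and baseline hopelessness". Baseline PHQ-9 is in neither list.

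Under Missing data handling, when more than a third of an outcome scale is missing, "researchers will not impute missing outcome data". The reason given is that the mixed model does not gain from it. No expected attrition rate appears anywhere.

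**The concern.** Week-4 PHQ-9 carries the primary comparison of each of 12 active conditions with the passive control. Sensitivity analyses 1 and 2 add covariates to the primary model and are not presented as dropout analyses. The weighted re-analysis is therefore the only planned re-estimation that targets dropout, and a preliminary test decides whether it is run.

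Such a gate can fail in two ways. It can open by chance, because many tests feed it. It can also stay shut when one arm really does lose more people, because a 12-degree-of-freedom test spreads its power over all 13 arms. Failing to reject is not evidence that loss is balanced. Equal loss rates can also hide different reasons for leaving, which a comparison of rates cannot detect. An undefined trigger adds discretion: .05 and .1 could both be defended after the data are seen.

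**Working it through.** **Inputs from the documents (Sample Size; Sensitivity analyses).** 500 in each of 12 active arms and 3 × 500 = 1,500 in passive control, so N = 12 × 500 + 1,500 = 7,500. Covariates listed: 10 + 5 = 15.

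**Assumptions.** Base attrition of 15%, 25% or 35%; one 500-person arm loses 5 or 10 points more than the other 12; *each covariate* means the 15 listed; tests are independent; evidence means p ≤ .05.

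**The plan's own figure.** None is given for attrition. As a check on arm sizes, the detectable effect for 500 against 1,500 at 90% power is (1.960 + 1.282) × √(1/500 + 1/1500) = 0.167, which agrees with the stated value of below 0.17.

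**1. Chance trigger with no differential attrition.** P(at least one of k tests) = 1 − 0.95^k.
- Condition test only (k = 1): 5%.
- Condition plus 10 demographic interactions (k = 11): 1 − 0.95^11 = 43%.
- Condition plus 15 interactions (k = 16): 1 − 0.95^16 = 56%.
- k = 16 at p ≤ .1: 1 − 0.90^16 = 81%.

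**2. Power of the condition test.** With one arm at p₀ + δ and the rest at p₀, the pooled rate is p̄ = p₀ + δ × 500/7,500. The noncentrality is λ = Σnᵢ(pᵢ − p̄)² / [p̄(1 − p̄)], referred to a 12-df noncentral chi-square with critical value 21.03.

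For δ = 0.05 the numerator is 500 × 7,000/7,500 × 0.05² = 1.167. At p₀ = 0.25, p̄ = 0.2533, λ = 1.167/0.1892 = 6.17 and power is 31%. For δ = 0.10 the numerator is 4.667.

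**3. Probability that the re-analysis is skipped.** If only the condition test counts, this is 1 − power. If any of 16 tests counts and the 15 interactions are null, it is (1 − power) × 0.95^15 = (1 − power) × 0.463.

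| Base | Excess | λ | Power, condition test | Skipped, condition test only | Skipped, any of 16 |
|---|---|---|---|---|---|
| 15% | 5 points | 8.99 | 45% | 55% | 25% |
| 25% | 5 points | 6.17 | 31% | 69% | 32% |
| 35% | 5 points | 5.11 | 25% | 75% | 35% |
| 15% | 10 points | 35.3 | 99% | 0.8% | 0.4% |
| 25% | 10 points | 24.5 | 94% | 6% | 3% |
| 35% | 10 points | 20.3 | 87% | 13% | 6% |

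**4. Simulation check.** At a base of 20%, 20,000 runs gave condition-test power of 36% for a 5-point excess and 95% for a 10-point excess. The formula gives 36% and 97%.

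**5. What the gate tells the reader.** Under the any-of-16 rule it fires 56% of the time with no difference, and 75%, 68% or 65% of the time with a 5-point excess. At p ≤ .1 it is skipped less often for a 5-point excess (5% to 13% over bases of 10% to 40%), but the chance trigger rises to 81%.

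**The case against.** **Dropout is not ignored.** A reader might infer that if the gate stays shut, nothing checks dropout. The documents do not support that. The attrition tests are themselves unconditional, all randomized participants are analysed, and the mixed model uses every observed value, with a stated reason for not imputing. Sensitivity analysis 2 adds 15 covariates, which helps in part where they predict both dropout and outcome. This stands: what is conditional is the one re-estimation that targets dropout.

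**Large imbalances would be caught.** A reader might infer that an arm with plainly heavier loss could pass unnoticed, or that the trigger carries almost no information. At a 10-point excess, skipping is unlikely under either rule (at most 13%). This stands, and it confines the concern to small and moderate excesses.

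**The two error rates must come from one rule.** It is tempting to set the 56% chance trigger beside the 55% to 75% skip risk. They belong to different rules: if only the condition test counts, the chance trigger is 5%; if any of 16 counts, the 5-point skip risk is 25% to 35%.

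**The bias missed may be small.** Suppose, at a 25% base, the extra 5 points lost differ by 0.5 SD at week 4 from those otherwise expected to remain. The observed arm mean shifts by 0.05 × 0.5/0.70 = 0.036 SD, or 0.07 at 1 SD, against a stated detectable effect of about 0.17. This illustration is fair and limits the severity.

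**The script may settle it.** The trigger, number of tests and weight model may be defined there, so the plan's text cannot establish that any of them is absent. This also stands.

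**Conclusion.** The point holds as a cheap improvement to a sensitivity analysis; it is not a flaw in the primary model. The weighted re-analysis is gated, nothing else in the document makes it unconditional, and the text does not define the trigger. Under an any-of-16 rule at .05, it appears by chance 56% of the time when attrition does not differ, and is missing 25% to 35% of the time when one arm loses 5 points more. If only the condition test counts, the 5-point skip risk is 55% to 75%. Its presence or absence is therefore a weak signal for small to moderate excess loss, and a reasonable one for an excess of about 10 points.

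These figures rest on assumed attrition rates, on reading evidence as a p-value criterion, on the 15 listed covariates being the ones tested, and on independence. Correlated covariates would usually lower the 56% and raise the any-of-16 skip risk.

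Weighting corrects only for dropout explained by the variables in the weight model. It does not address dropout that depends on unobserved week-4 symptoms, so running it always gives consistent reporting and limited extra protection.

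**What to change.** In item 3, remove the condition. Suggested wording: *At least the primary analysis will be re-run with inverse probability weighting regardless of the results of the attrition tests. Attrition will be reported descriptively by arm.*

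In the same item, list the weight-model variables and confirm that baseline PHQ-9 is among them, since it is absent from both covariate lists; the script may already include it. State that standard errors will allow for the weights, for example robust or bootstrap.

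The cost is a few lines of text and one more set of results from an analysis already planned. The Data Collection section says that data collection has not started, so on the document's own account the change can be made before any outcome is seen.

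### The d = 0.19 given for comparisons between intervention conditions does not follow from the inputs that give d = 0.17: at 90% power, 500 versus 500 detects about 0.205

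*Combined protocol and SAP*

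**What the plan says.** All the relevant statements are in the combined protocol and SAP.

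- **Sample Size, arm sizes.** "Researchers will aim to recruit 500 participants per intervention condition", while "the passive control condition will have 3X as many participants as the other conditions". That is 500 per intervention condition and 1,500 in passive control. The total is 12 × 500 + 1,500 = 7,500, which agrees with the stated total.
- **Sample Size, statement on passive control.** For an intervention condition against passive control, the detectable effect is put below d = 0.17, "with 90% power and alpha = 0.05".
- **Sample Size, statement on intervention conditions.** The next sentence presents a further property of the same sample: it can "detect differences in change in depressive symptoms from baseline to follow-up between each intervention condition smaller than $d = 0.19". Neither power nor alpha is restated.
- **Inference Criteria.** "Two-sided tests will be used for all analyses".
- **Secondary analyses, item 1.** To compare each experimental SSI with the active comparison SSI on PHQ-9, "researchers will redo the main analysis, except using the active comparison condition as the comparator". This is the 500 versus 500 comparison that the statement on intervention conditions describes.

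The document gives no SD, baseline to follow-up correlation or attrition rate for either figure.

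**The concern.** The two claims come one after the other and describe one sample, so a reader will apply the 90% power and alpha 0.05 of the first to the second. The second comparison replaces a control group of 1,500 with one of 500, which raises the standard error by a known factor. The step from 0.17 to 0.19 looks too small for that change.

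The 0.19 is the only sensitivity figure the plan gives for the 11 comparisons of an experimental SSI with the active comparison SSI on PHQ-9 (Secondary Hypotheses, item 1). If it is too favourable, a null result against the active SSI will be read as stronger evidence against a difference of that size than the design supports.

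**Working it through.** **Inputs.** From Sample Size: 500 per intervention condition, 1,500 in passive control, power 90%, alpha 0.05. From Inference Criteria: two-sided tests. Assumed, because the document is silent: a two-sample comparison of mean change, d on the SD of change, and no attrition.

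**Formula.** Detectable d = (z for alpha/2 + z for power) × √(1/n₁ + 1/n₂). The multiplier at 90% power is 1.960 + 1.2816 = 3.2415.

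**1. The passive-control figure.** 500 versus 1,500: 3.2415 × √(1/500 + 1/1500) = 3.2415 × 0.05164 = **0.1674** (noncentral t: 0.1675). This is below 0.17, and power at d = 0.17 is 90.9%. The plan's passive-control figure is reproduced.

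**2. The figure between intervention conditions, same inputs.** 500 versus 500: 3.2415 × √(2/500) = 3.2415 × 0.06325 = **0.2050** (noncentral t: 0.2052). This is not below 0.19.

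**3. Power at d = 0.19, 500 versus 500.** Φ(0.19/0.06325 − 1.960) = Φ(1.044) = **85.2%** (noncentral t: 85.1%).

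**4. Sample size for 90% power at d = 0.19.** 2 × (3.2415/0.19)² = 582.1, so **583** per condition (noncentral t: 584), against 500 planned.

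**5. Ratio of the two figures.** If both use the same alpha, power, SD definition and proportional attrition, those terms cancel. The ratio must be √[(2/500)/(1/500 + 1/1500)] = √1.5 = 1.225. The stated ratio is 0.19/0.17 = 1.118. Allowing for rounding it is at most 0.195/0.165 = 1.18. As rounded point values, the two figures cannot share one basis.

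**6. Which bases would bring 500 versus 500 below 0.19?**

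| Basis | 500 vs 500 | 500 vs 1,500 | In the document? |
|---|---|---|---|
| 90% power, two-sided, SD of change | 0.205 | 0.167 | Power, alpha and sidedness stated; SD basis not |
| 85% power, two-sided, SD of change | 0.1895 | 0.155 | 85% not stated |
| 90% power, one-sided, SD of change | 0.185 | 0.151 | Excluded by Inference Criteria |
| 90% power, two-sided, raw-score SD, change score, correlation 0.571 | 0.190 | 0.155 | Correlation not stated |

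For the last row, the SD-of-change result is multiplied by √(2(1 − r)). Requiring 0.2050 × √(2(1 − r)) ≤ 0.19 gives r ≥ 0.571.

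**7. Attrition (assumed rates).** With 10% loss (450 versus 450), power at d = 0.19 is 81.3%. With 20% loss (400 versus 400), it is 76.6%. The same losses move the passive-control figure to 0.176 and 0.187, so attrition worsens both figures and does not explain the gap between them.

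**The case against.** The strongest reply is that both figures are worded as upper bounds and neither has a stated basis. A bound of 0.17 is met by any smaller value, so obtaining 0.167 does not prove how it was derived, and the ratio argument binds only if both figures are rounded point values. The document does not say that d is on the SD of change. On the raw-score SD, with a baseline to follow-up correlation slightly above 0.57, both statements are literally true at 90% power (about 0.155 and just under 0.19). A baseline-adjusted calculation would need a lower correlation: it gives 0.196 at 0.3 and 0.188 at 0.4. In addition, the 90% is attached in the text only to the passive-control sentence. At 85% power the 0.19 is correct, and the fault would be an omitted power level.

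Part of this stands. The basis of the 0.19 cannot be known from the document, and the conclusion must be limited to the inputs that yield 0.17. It does not rescue the sentence as written. Neither the 85% nor any correlation appears in the plan. Each route that brings the second figure under 0.19 also takes the first well below 0.17, so 0.17 would no longer be the figure the stated inputs produce. A change of power between adjacent sentences about one sample would itself need to be disclosed.

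It is also fair to say that the effect is small and confined to secondary comparisons, and that attrition is a separate matter affecting both figures.

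**Conclusion.** The concern holds. On the plan's stated power, alpha, two-sided testing and arm sizes, with d on the SD of change and no attrition, the design detects about d = 0.205 between two intervention conditions at 90% power, not less than 0.19. The gap is 0.205 − 0.19 = 0.015 in d. At d = 0.19, power is about 85%, so the chance of missing a true difference of that size is about 15% and not 10%. Reaching 90% there would take 583 − 500 = 83 more analysed participants per condition.

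This is a modest error in the stated sensitivity of secondary analysis 1. It does not alter any estimate or p-value, or the primary passive-control figure before attrition. The arithmetic is firm. What remains open is whether the authors used an undocumented basis for the 0.19.

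**What to change.** Replace the sentence on differences between intervention conditions in Sample Size with one of these:

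- *With 500 per condition, 90% power and two-sided alpha 0.05, a difference of about d = 0.21 between two intervention conditions is detectable.*
- *With 500 per condition and two-sided alpha 0.05, a difference of d = 0.19 between two intervention conditions is detectable with about 85% power.*

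In either case, state that d is on the SD of change and that both this figure and the passive-control figure assume no attrition. If the 0.19 was in fact derived on the raw-score SD, keep it but state the assumed baseline to follow-up correlation and give the passive-control figure on the same basis (about 0.155 at a correlation of 0.57).

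The cost is one corrected sentence. Enrolment and analyses do not change; the stated sensitivity of the comparisons with the active SSI becomes slightly less favourable.
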